9. DATA SCREENING AND ACCEPTANCE

9.1 General Principles

The objective of the data screening is to assess the quantity, quality and statistical characteristics of the data relative to the requirements of the planned analyses.

9.2 Data Handling and Electronic Transfer of Data

Amgen's Clinical Data Management department will provide all data to be used in the planned analyses. The database will be subject to edit checks outlined in the Clinical Data Management Plan (DMP). See details of this section in the DMP.

9.3 Handling of Missing and Incomplete Data

The following imputation for missing or incomplete data will be performed if required:

Incomplete adverse event and concomitant medication dates missing data will be imputed as described in Appendix A.

Non-pharmacokinetic measurements (eg. biomarker data) that are below the lower limit of quantification will be considered equal to half of the lower limit of quantification for all analyses unless specified otherwise.

Please refer to section 10.8 for details of handling missing or incomplete PK concentration data.

9.4 Detection of Bias

Lack of protocol compliance and the potential for biased statistical analyses will be examined by assessing the incidence of important protocol deviations in each cohort. The clinical study team will identify and document the criteria for important protocol deviations.

9.5 Outliers

Outlier data will not be excluded unless scientifically justified.

PK plasma concentration data will be evaluated for outliers by visual inspection and decisions to re-assay individual samples will be made in accordance with standard PKDM practices.

9.6 Distributional Characteristics

Where appropriate, the assumptions underlying the proposed statistical methodologies will be assessed. If required data transformations or alternative non-parametric methods of analyses will be utilized.

9.7 Validation of Statistical Analyses

Programs will be developed and maintained, and output will be verified in accordance with current risk-based quality control procedures. Tables, figures and listings will be produced with validated standard macro programs where standard macros can produce the specified outputs.

The production environment for statistical analyses consists of Amgen-supported versions of statistical analysis software, for example the SAS System and S-plus.

10. STATISTICAL METHODS OF ANALYSIS

10.1 General Principles

Descriptive statistics will be provided for selected demographic, safety, PK, PD, and biomarker data by dose schedule and time as appropriate. Descriptive statistics on continuous data will include means, medians, SDs, and ranges, while categorical data will be summarized using frequency counts and percentages. Graphical summaries of the data may also be presented. When data are summarized by time, the values recorded against the scheduled time points listed in the protocol will be used. When assessing minimum/maximum increases or decreases over the study, all assessments, including unscheduled assessments will be used. In general, data listings will be sorted by dose, subject, and time.

The primary analysis is planned after all dose-escalation cohorts and dose-expansion subjects have had the opportunity to complete 6 months of treatment.

A final analysis is planned after all dose-escalation cohorts and dose-expansion subjects have ended the study.

10.2 Subject Accountability

The number and percent of subjects who were screened, enrolled, received investigational product, completed investigational product, discontinued from investigational product (including reasons for discontinuing), completed study, discontinued the study (including reasons for discontinuing) will be summarized by dose schedule and time.

Key study dates for the first subject enrolled, last subject enrolled, last subject's end of study will be presented.

A subject listing and summary noting inclusion in each analysis subset will be provided for all subjects enrolled. A subject listing noting duration of AMG 211 administration, reason for discontinuation of treatment, and reason for discontinuing the study will be provided. A list of subjects screened but not enrolled (screen failures) will be provided.

10.3 Important Protocol Deviations

Important Protocol Deviations (IPDs) categories are defined by the study team before the first

patient visit and updated during the IPD reviews throughout the study prior to database lock. If a snapshot is being taken during the study rather than a database lock at the end of the study, categories should be updated during the IPD reviews throughout the study prior to database lock. These definitions of IPD categories, sub-category codes and descriptions will be used during the course of the study. The final IPD list is used to produce the Summary of IPDs table and the List of Subjects with IPDs. In addition, a separate listing of all inclusion and exclusion deviations will be provided.

10.4 Demographic and Baseline Characteristics

Demographic (ie, age, age groups [< 65 , ≥ 65 and ≥ 75], sex, race, ethnicity, and baseline characteristics (height, weight, and Karnofsky performance status) will be summarized by dosing schedule and overall using descriptive statistics. If multiple races have been reported for a subject, the subject will be categorized as multiple races as well as by the combination of races.

A listing of the demographic and baseline characteristics will be provided. In addition listings of medical history (including antecedent hematologic or oncologic disease, other diseases/symptoms such as fatigue, bleeding, and infection whether resolved and ongoing), surgical history, prior anti-cancer usage and prior radiotherapy usage will be provided.

10.5 Safety Analyses

10.5.1 Adverse Events

The Medical Dictionary for Regulatory Activities (MedDRA) version 16.0 or later will be used to code all adverse events to a system organ class and a preferred term. The subject incidence of adverse events will be summarized for all treatment-emergent, serious treatment emergent, treatment-related, serious treatment-related, those leading to withdrawal of investigational product or other protocol-required therapies, fatal adverse events, and significant treatment emergent adverse events. The identification of significant adverse events is a continuous process. Events may be identified and documented as the safety profile of the drug is characterized. The severity of each adverse event will be graded using CTCAE version 4.03 criteria.

Subject incidence of all treatment-emergent, serious, treatment-related, serious treatment-related, those leading to withdrawal of investigational product or other protocol-required therapies, significant treatment-emergent adverse events, and fatal adverse events will be tabulated by system organ class and preferred term in descending order of frequency. Where appropriate the tables will also be presented by worst grade. The above adverse event tables will not be created if two or fewer subjects experience the adverse event.

Details of each adverse event will be listed. Listings and/or narratives of any on-study deaths, serious and significant treatment-emergent adverse events, including early withdrawals due to adverse events, also will be provided should they occur.

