10.2 Sample Size Considerations

It is anticipated that approximately 78 subjects will be enrolled in this study.

Approximately 39 subjects will be enrolled in the dose-escalation cohorts and approximately 39 subjects will be enrolled in the dose-expansion cohorts.

The sample size in dose-escalation cohort is determined empirically and is consistent with this type of study using a modified TPI Bayesian model design (Bailey et al, 2009; Neuenschwander et al, 2008).

Refer to [Appendix E](#) for details of the modified TPI Bayesian model, the average sample size, and other design operating characteristics.

In the dose-escalation cohorts, with 3 DLT-evaluable subjects per dose level, there is a 49% to 73% probability of observing at least 1 DLT if the true DLT rate is 20% to 35%.

In the dose-expansion cohorts, with 39 subjects there is a 86% probability of observing at least one adverse event with 5% incidence rate. In the dose-expansion cohorts, an exact 80% binomial confidence interval (CI) will be provided for the ORR. With 39 subjects and 20.5% ORR, the expected 80% CI and its half-width would be 12.3% to 31.2% and 9.5%, respectively.

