10.4.2.1 Safety Endpoints

10.4.2.1.1 Adverse Events

Subject incidence of all treatment-emergent adverse events (TEAEs) will be tabulated by system organ class (SOC) and preferred term (PT). The number and percentage of subjects reporting adverse events will be evaluated overall and by dose level and will also be tabulated by relationship to study drug.

Tables of fatal adverse events, serious adverse events, adverse events leading to withdrawal from investigational product or other protocol-required therapies, and Events of Interest (EOI) will also be provided.

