10.5.1.1 Dose Limiting Toxicities

The analysis of the probability of dose limiting toxicities (DLT) will be based on the Dose Escalation Analysis Set defined in [Section 7.3](#). A listing and summary of the subject incidence of dose limiting toxicities (DLT) will be provided should they occur.

The planned primary nominal doses are 200, 400, 800, 1600, 3200 and 6400 µg/d. Potential intermediate doses with a 2- fold increment and a 50% reduction from the starting dose will be considered after DLT is observed. The dose-escalation cohorts will use a TPI Bayesian design to guide dose escalation. The MTD target TPI for DLT is (0.20, 0.35), and TPIs of (0.35, 0.60) and (0.60, 1.00) are defined as excessive and unacceptable, respectively. The design seeks to identify a dose most likely to have a DLT rate in the target TPI, but with overdose control that limits the possibility that the dose has an excessive or unacceptable DLT rate ([Babb et al, 1998](#)). The probability of a DLT at dose level d_i is assumed to follow a Bernoulli distribution with probability p_i where the logit of p_i increases linearly with the log of the standardized dose in the following 2-parameter logistic model:

$$\log [p_i / (1-p_i)] = \text{logit}(p_i) = \log[a] + \exp(\log[b]) \log (d_i / d_{\max})$$

where a and b are random variables and d_{\max} is the maximum planned dose.

The probability of each TPI and of a DLT will be summarized by dose along with the estimated dose-toxicity curve. A final estimate of the MTD will be estimated from the TPI Bayesian model utilizing all DLT-evaluable subjects. Please refer to [Appendix C](#) for more details on the TPI model and its operation characteristics.

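### SAP 10.5.1 sets a minimum count of three subjects, with its unit undefined, for adverse event tables that Protocol 10.4.2.1.1 promises without any minimum

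*SAP*

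**What the plan says.** SAP 10.5.1 plans one incidence table for each of several categories: all treatment-emergent, serious, related, serious related, leading to withdrawal, significant, and fatal. The end of that list reads "significant treatment-emergent adverse events, and fatal adverse events will be tabulated by system organ class and preferred term in descending order of frequency". A cutoff follows: "The above adverse event tables will not be created if two or fewer subjects experience the adverse event". As worded, it covers every table just named.

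The same section keeps two other outputs: "Details of each adverse event will be listed", and "Listings and/or narratives of any on-study deaths, serious and significant treatment-emergent adverse events, including early withdrawals due to adverse events, also will be provided". SAP 10.5.1.1 handles dose-limiting toxicities separately with no minimum count: "A listing and summary of the subject incidence of dose limiting toxicities (DLT) will be provided should they occur".

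Protocol 10.4.2.1.1 commits to tabulating the subject incidence of all treatment-emergent events by system organ class and preferred term, to evaluating the counts overall and by dose level, and to tabulating them by relationship to study drug. It further commits to "Tables of fatal adverse events, serious adverse events, adverse events leading to withdrawal from investigational product or other protocol-required therapies". No minimum count is attached to any of these. Protocol 10.1.1 makes subject incidence of treatment-emergent events part of the primary endpoint. SAP 10.9 states that nothing departs from the protocol's analyses.

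**The concern.** The SAP places a condition on primary-endpoint tables that the protocol does not contain, and does not declare it. The age of the SAP does not explain this. It was written for the protocol dated 24 March 2014, but the text of 10.4.2.1.1 that Amendment 3 replaced also had no minimum.

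The sentence is also incomplete as a rule. The adverse event it refers to could be a preferred term or a table's whole category. The count of two could be taken over all subjects or within a dose level. Two programmers could follow it faithfully and produce different safety sections.

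What is at stake is the numerator, denominator and dose-level incidence for uncommon but serious events. In a phase 1 trial with cohorts of 3 to 6 subjects, one or two affected subjects is an ordinary count. The SAP's own laboratory rule in 10.5.2.1 is less restrictive: a parameter enters the toxicity summary once a single subject has a grade 3 or higher value.

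**Working it through.** **Inputs.** Cutoff: no table at two or fewer subjects, so at least three are needed (SAP 10.5.1). Expansion size 39 and event rate 5% (Protocol 10.2). Total size about 78 (Protocol 10.2) or up to 34 (SAP 3.2). Cohort size 3 to 6 (Protocol Table 3). Rates of 2%, 10% and 20% are illustrative assumptions; 5% is the protocol's figure.

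**Step 1: reproduce the plan's figure.** Protocol 10.2 says that with 39 subjects "there is a 86% probability of observing at least one adverse event with 5% incidence rate". With X binomial, P(X ≥ 1) = 1 − 0.95^39 = 0.865. The stated figure reproduces.

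**Step 2: category reading.** A category table is skipped if two or fewer subjects fall in that category. The protocol and SAP then give different outputs:

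| Subjects with a fatal (or serious, or withdrawal) event | Protocol 10.4.2.1.1 | SAP 10.5.1 |
|---|---|---|
| 1 or 2 | table | listing and/or narrative only |
| 3 or more | table | table |

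A fatal event would still be counted in the all-treatment-emergent table. It would be identifiable there as fatal only if a worst-grade version is made, which the SAP plans only where appropriate.

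**Step 3: per-term reading.** A term that occurs is left out when X is 1 or 2, and P(1 ≤ X ≤ 2) = P(X ≥ 1) − P(X ≥ 3). For n = 39 and p = 0.05:

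- P(X = 1) = 39 × 0.05 × 0.95^38 = 0.278
- P(X = 2) = 741 × 0.05² × 0.95^37 = 0.278
- P(1 or 2) = 0.555
- P(X ≥ 3) = 0.309
- Share of occurrences left untabulated = 0.555 / 0.865 = 64%

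Other settings on the same reading:

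| n | Rate | Occurs in only 1 or 2 subjects | Reaches a table |
|---|---|---|---|
| 34 | 5% | 58.5% | 24.1% |
| 39 | 2% | 50.2% | 4.3% |
| 39 | 10% | 22.1% | 76.2% |
| 78 pooled | 2% | 58.8% | 20.5% |
| 78 pooled | 5% | 22.7% | 75.4% |
| 78 pooled | 10% | 1.2% | 98.7% |

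For an 86% chance of reaching a table, the true rate would have to be about 11.9% with 39 subjects, or 6.1% with 78.

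**Step 4: overall or per dose level.** Two subjects are 2/78 = 2.6% of the whole trial, 2/39 = 5.1% of the expansion, 2/6 = 33% of a full cohort and 2/3 = 67% of an initial cohort. If the cutoff were applied per term within a 6-subject cohort at an assumed 20% rate, the chance of one or two cases is 63.9% and of three or more 9.9%.

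**Step 5: an example from the documents.** Protocol 2.2.4 reports the first-in-human study of the same drug. Grade 3 related events affected 5 patients, with each term seen in 1 or 2. Serious related events also affected 5 patients, with each term having 1 or 2 events. Per term, none of those terms would be tabulated. Per category, both tables would be made, since 5 exceeds 2. The choice of reading therefore changes the output completely.

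**The case against.** The strongest reply is that the sentence speaks of whole tables not being created. That fits the category reading better; a per-term filter would more naturally say that terms are not displayed. On the category reading the all-treatment-emergent table is almost certain to exist with 34 to 78 treated subjects, and single-case terms would appear in it. The documents give no such counts for this trial, so this is an inference, but a safe one. The probabilities in steps 3 and 4 then do not describe what happens.

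Nothing disappears from the report either. Every event is listed, SAP 10.1 generally sorts listings by dose, and with one or two cases a reader who knows the cohort size can work out the incidence. Dose-limiting toxicities have their own summary. Dose decisions rest on the outputs in SAP Appendix D and the review in Protocol 10.3.2, which covers all grade 3 or higher toxicities, so they do not depend on these tables. The figure of 39 also belongs to the current protocol; SAP 3.2 plans 10 expansion subjects.

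All of this stands and limits the size of the point. It does not remove the conflict: on the category reading too, a promised fatal, serious or withdrawal table with one or two affected subjects is not produced. A listing lets a reader reconstruct an incidence, but it is not the table that the protocol promises.

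**Conclusion.** The point holds at moderate size. The SAP sets an undeclared minimum count that the protocol lacks, and leaves its unit open in two ways. The conflict over sparse fatal, serious and withdrawal tables exists on either reading. The wider loss, 55.5% untabulated against 30.9% tabulated for a 5% event in 39 subjects, applies only if the cutoff works per preferred term. The 63.9% figure further assumes that it works within a cohort and that the rate is 20%.

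A reader might infer that serious and related events will be missing from the primary safety summaries, or that the reported safety profile is biased toward looking cleaner. The documents do not support either as a general statement. The first follows only on the per-term reading, and for the second, no event leaves the report. What is lost is incidence tabulation of a primary endpoint.

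**What to change.** Delete the sentence from SAP 10.5.1. Alternatively, limit it to tables with no events, and state that the fatal, serious, treatment-related and withdrawal tables are always produced, overall and by dose level, in line with Protocol 10.4.2.1.1.

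If the sponsor wants to keep a cutoff, the SAP should define its unit (term or category, overall or dose level), restrict it to non-serious terms, and declare it in SAP 10.9 as a change from the protocol.

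The cost is one sentence in the SAP and a few short tables, some of them sparse. No data collection or design element changes.

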10.5.1.1 Dose Limiting Toxicities

The analysis of the probability of dose limiting toxicities (DLT) will be based on the Dose Escalation Analysis Set defined in [Section 7.3](#). A listing and summary of the subject incidence of dose limiting toxicities (DLT) will be provided should they occur.

The planned primary nominal doses are 200, 400, 800, 1600, 3200 and 6400 µg/d. Potential intermediate doses with a 2- fold increment and a 50% reduction from the starting dose will be considered after DLT is observed. The dose-escalation cohorts will use a TPI Bayesian design to guide dose escalation. The MTD target TPI for DLT is (0.20, 0.35), and TPIs of (0.35, 0.60) and (0.60, 1.00) are defined as excessive and unacceptable, respectively. The design seeks to identify a dose most likely to have a DLT rate in the target TPI, but with overdose control that limits the possibility that the dose has an excessive or unacceptable DLT rate ([Babb et al, 1998](#)). The probability of a DLT at dose level d_i is assumed to follow a Bernoulli distribution with probability p_i where the logit of p_i increases linearly with the log of the standardized dose in the following 2-parameter logistic model:

$$\log [p_i / (1-p_i)] = \text{logit}(p_i) = \log[a] + \exp(\log[b]) \log (d_i / d_{\max})$$

where a and b are random variables and d_{\max} is the maximum planned dose.

The probability of each TPI and of a DLT will be summarized by dose along with the estimated dose-toxicity curve. A final estimate of the MTD will be estimated from the TPI Bayesian model utilizing all DLT-evaluable subjects. Please refer to [Appendix C](#) for more details on the TPI model and its operation characteristics.

10.5.2 Laboratory Test Results

10.5.2.1 Chemistry, Hematology and Coagulation

Individual chemistry, hematology and coagulation laboratory data will be listed and select parameters of interest plotted. Values outside the normal laboratory reference ranges will be flagged as high or low on the listings. CTCAE grades will also be highlighted where appropriate. Unscheduled assessments will be incorporated in the laboratory analyses where possible.

The number and percentage of subjects experiencing treatment emergent laboratory toxicities with worst post dose CTCAE grades of ≥ 1 , ≥ 2 , ≥ 3 and 4 will be presented. The direction of the laboratory worsening will be denoted. The summary will be presented for all laboratory

parameters for which at least one subject experienced a treatment emergent toxicity with a worst grade ≥ 3 .

Additionally, the number and percentage of subjects experiencing 1, 2, 3 and 4 worsening CTCAE grade shifts from baseline will be presented. The direction of the laboratory worsening will again be denoted.

Shifts tables indicating the change between the baseline and the maximum post dose CTCAE grades for an increased value, and the maximum post dose grade for a decreased value will be provided for selected laboratory parameters of interest.

A listing of CTCAE grade 3 or higher laboratory toxicities will be provided. This listing will include all laboratory data for the subject and laboratory parameter of interest in order to provide proper context. A flag will indicate the grade 3 or higher toxicity.

Summaries of the absolute value and/or changes from baseline at each scheduled assessment will be provided for selected laboratory parameters of interest.

A summary of the change from baseline to the post dose maximum, time to post-dose maximum, change from baseline to the post dose minimum, and the time to the post dose minimum may also be provided for selected parameters of interest.

Potential Hy's law cases will be listed and may also be summarized.

10.5.2.2 Urinalysis

Individual urinalysis data will be listed and select parameters of interest plotted.

Blood, protein, glucose and ketones will be graded in the following manner: 0='0 or Trace', 1='1+', 2='2+', 3='3+', 4='4+'. Microscopic parameters (WBC, epithelial cells, bacteria, casts, crystals) will be graded in the following manner: 0='0-4 none, rare, occasional', 1='5-50 moderate, few', 2='>50 many, heavy, too numerous to count'.

The number and percent of subjects with a worst post-dose presence of blood in the urine of '0 or Trace', '1+', '3+', or '4+' will be presented (also for protein, glucose, and ketones in the urine).

Summaries of the absolute value and/or changes from baseline at each scheduled assessment will also be provided.

10.5.3 Vital Signs

Vital signs will be listed for each subject. The analysis of vital signs will include summary statistics at selected time points for each subject. Shifts in vital sign values from baseline over time will be tabulated for each subject.

10.5.4 **Electrocardiogram (ECG)**

All on-study electrocardiogram (ECG) data will be listed and select parameters of interest may be plotted.

Summaries over time and/or changes from baseline over time will be provided for all 12-lead ECG parameters.

The analysis of Fridericia's (QTcF) QT correction will use the results recorded on the CRF. Subjects' maximum change from baseline in QT interval corrected by Fridericia's formula will be categorized into the following groups per their maximum change from baseline in QTcF.

Unscheduled assessments will be included in the determination of the maximum change.

- <=30 msec
- >30 – 60 msec
- >60 msec

The number and percentage of subjects in each group will be summarized.

Subjects will also be categorized into the following groups per their maximum post baseline QTcF. Unscheduled assessments will be included in the determination of the maximum post baseline value.

- <=450 msec
- >450 – 480 msec
- >480 – 500 msec
- >500 msec

The number of subjects in each group will be summarized for each dosing group.

In addition, the relationship between plasma concentration of AMG 211 and change from baseline in QTcF will be explored graphically.

